Participants will also be followed up at 3-months and at 6-months to assess clinical outcomes and treatment acceptability. Study measures are shown in Table 1. Secondary smoking outcomes will include 7- and 30-day point prevalence abstinence at each assessment. Abstinence will be verified by salivary cotinine assay (≤ 10 ng/ml), which improves self-report validity. When in-person visits are allowed post-COVID-19 pandemic, participants will also be asked to provide expired carbon monoxide (CO) breath readings at baseline, post-treatment, and 3- and 6-month follow-up.

Tobacco Cessation Treatment Preferences among Veteran Smokers

Following treatment completion for each cohort of $n = 5$ participants, qualitative data will be analyzed and based upon results, the intervention structure and content will be revised. Intervention content that may be subject to revision includes the computerized algorithms, CBT module content, and content and timing of SMS text messages.

Table 1. Aim 3 Measures

Measure	No. Items	Completed by	Month				Sessions
			0	Quit Date	3	6	
BACKGROUND AND PROCESS VARIABLES							
1. Demographics	32	Self-report	X	-	-	-	-
2. Smoking history/current smoking	6	Self-report	X	-	-	-	-
3. HIV Disease Progression – CD4, Viral Load (EMR)	-	Self-report	X	-	-	-	-
4. Fagerstrom Test for Nicotine Dependence	7	Self-report	X	-	-	-	-
5. The Everyday Discrimination Scale	10	Self-report	X	-	-	-	-
6. Pain, Enjoyment of Life, and General Activity (PEG) Scale	3	Self-report	X	-	X	X	-
7. Smoking and Nicotine Knowledge	14	Self-report	X	-	X	-	-
8. Non-VA Treatment Utilization	9	Self-report	X	-	X	X	-
TREATMENT PERSONALIZATION MEASURES							
9. Smoking Cessation Motivation	1	Self-report	X	X	X	X	-
10. Smoking Cessation Self-Efficacy	1	Self-report	X	X	X	X	-
11. Stages of Change	2	Self-report	X	-	X	X	-
12. PTSD Checklist of DSM-5 (PCL-5)	20	Self-report	X	-	X	X	-
13. Patient Health Questionnaire (PHQ-9)	9	Self-report	X	-	X	X	-
14. Alcohol Use Disorders Identification Test (AUDIT-C)	3	Self-report	X	-	X	X	-
15. Non-Cigarette Smoking Behavior	6	Self-report	X	-	X	X	-
16. Smoking Cessation Weight-Grain Concerns	2	Self-report	X	-	-	-	-
17. Smoking to Cope with Pain	1	Self-report	X	-	-	-	-
18. Exposure to Smoking Cues	1	Self-report	X	-	-	-	-
19. Pharmacotherapy Adherence – Visual Analog Scale (personalized to pharmacotherapy use)	1-3	Self-report	-	X	X	X	-
20. Tobacco Exposure Questionnaire	6	Self-report	X	-	X	X	-

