Tobacco Cessation Treatment Preferences among Veteran Smokers

CLINICAL MEASURES							
21. 7-day, 30-day Point Prevalence Abstinence	2	Research Interventionist	X	-	X	X	-
22. Prolonged Abstinence	2	Research Interventionist	-	-	X	X	-
23. Timeline Follow-back (cigarettes per day)	1	Research Interventionist	-	-	X	X	-
OUTCOME MEASURES							
24. Patient Recruitment	-	Research Interventionist	X	-	-	-	-
25. Treatment Retention	-	Research Interventionist	-	X	X	X	-
26. Withdrawals	-	Research Interventionist	X	X	X	X	-
27. Patient Satisfaction – Treatment Acceptability	8	Self-report	-	X			X
28. Therapist Satisfaction – Treatment Feasibility	7	Research Interventionist's Self-report	-	X			X
29. Clinician Time	4	Research Interventionist	X	X	-	-	-

Mesh Treatment Components

Treatment Personalization Algorithm. During session 1, the interventionist will complete a treatment personalization algorithm with the participant. This algorithm requires participant self-report data in addition to data from the electronic health record. Data inputs are shown in Table 2.

Table 2. Treatment Personalization Algorithm Components

ALGORITHM	CONSTRUCT	MEASURE
Baseline CBT Algorithm	Motivation; Self-efficacy, Social influences; Substances and Alcohol; Mental Health; Pain; Pharmacotherapy	Smoking Cessation Motivation; Smoking Cessation Self-Efficacy; Stages of Change; PTSD Checklist of DSM-5 (PCL-5); Patient Health Questionnaire (PHQ-9); Alcohol Use Disorders Identification Test (AUDIT); Non-Cigarette Smoking Behavior; Smoking to Cope with Pain; Exposure to Smoking Cues
Quit Week CBT Algorithm	Relapse prevention; Weight gain; Self-efficacy; Motivation; Pharmacotherapy adherence;	Relapse Situation Efficacy Questionnaire (RSEQ); Smoking Cessation Weight-Grain Concerns; Pharmacotherapy Adherence – Visual Analog Scale (personalized to pharmacotherapy use); If necessary: Smoking Cessation Motivation; Smoking Cessation Self-Efficacy; Stages of Change

Tobacco Cessation Treatment Preferences among Veteran Smokers

Post-Quit Relapse-Prevention Messaging Algorithm	Preferences regarding message type: Inspirational; Medication reminders; Help with lapses; Trigger information; Behavioral skills	Preference ratings
Baseline Pharmacotherapy	Willingness; Preference; Contraindications	Self-report
Quit Week Pharmacotherapy	Status; Adherence; Willingness	Self-report
Quit Week Algorithm for Revising Pharmacotherapy Regimen (Initially Prescribed Dual-NRT)	Willingness; Contraindications	Self-report

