Quit Week Algorithm for Revising Pharmacotherapy Regimen (Initially Prescribed Varenicline)	Willingness; Preference	Self-report
Quit Week Algorithm for Revising Pharmacotherapy Regimen (Initially Prescribed Bupropion)	Willingness; Preference	Self-report
Quit Week Algorithm for Revising Pharmacotherapy Regimen (Initially Prescribed Single-Formulation NRT)	Willingness; Preference; Contraindications	Self-report

Personalized Smoking Cessation Facilitation Meetings. Mesh facilitators will meet with participants between 5 to 7 sessions. For completion of stop smoking facilitation sessions, participants will be offered the choice of whether to complete sessions using a personal telephone, a personal digital device (i.e., tablet, laptop, or desktop computer with webcam), or a VA-issued digital device (i.e., 4G-enabled tablet with webcam). For those who request a VA-issued personal digital device, a consult will be placed to Prosthetics Service to issue the Veteran a 4G-enabled tablet in order to complete subsequent counseling sessions via VA Video Connect.

Core CBT modules include: identifying reasons for quitting, setting a quit date, breathing relaxation technique, identifying smoking triggers, identifying social support, and education about relapse prevention. We will also use the Session 1 treatment personalization algorithm to individually tailor counseling to provide an adaptable selection of discrete counseling modules in addition to core modules that all participants will receive. CBT treatment personalization algorithms are based upon the following assessments: self-efficacy, motivation for quitting, depression, PTSD, alcohol use, comorbid non-cigarette smoking, tobacco exposure, smoking to cope with pain, adherence to pharmacotherapy, and concerns about weight gain. Two to three of these 5- to 15-minute modules will be included in each session, and modules will focus on building each participant's skills that are needed to achieve cessation and long-term abstinence. Optional modules will address low motivation to quit, low self-efficacy for quitting and relapse prevention, comorbid psychiatric concerns, alcohol/drug use, tobacco exposure and poly-tobacco use, pain management, pharmacotherapy adherence, and healthy eating/exercise. Each session will last 30-60 minutes.

Tobacco Cessation Treatment Preferences among Veteran Smokers

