At Session 3 (1 week post-quit), the participant will be asked several treatment personalization questions (see Table 1). These responses will be entered into the treatment personalization algorithm to determine additional post-quit modules depending on the following: self-reported quit status at Session 3 (defined as complete abstinence since most recent quit date), self-efficacy, motivation, pharmacotherapy adherence, and barriers to abstinence. Additional modules to be added to counseling include: relapse prevention, motivational interviewing, decisional balance, pharmacotherapy adherence (or pharmacotherapy motivational interviewing), and review of barriers and protective factors.

Personalized Smoking Cessation Pharmacotherapy. Participant pharmacotherapy recommendations will be based upon the study treatment personalization algorithm and will be sent to the participant's clinic team. All pharmacotherapy prescriptions will be managed as part of routine clinical care by the participant's VA healthcare providers, who may choose to follow study pharmacotherapy recommendations at their discretion.

At the baseline session, a study staff member will ask questions regarding tobacco cessation pharmacotherapy preferences and contraindications directly to the study participant. The interventionist will also review the participant's electronic medical record to note any additional potential contraindications to pharmacotherapy. Pharmacologic recommendations will be based upon a recent meta-analysis of smoking cessation pharmacotherapy as well as VA Pharmacy Benefits Management Services guidelines (Cahill et al., 2013). Similar to Cropsey et al.'s (2015) algorithm methodology, participants will be followed 1 week post-quit to assess abstinence and pharmacotherapy adherence. If they are using tobacco and have poor adherence (<70% adherence) and are willing to increase pharmacotherapy use, then adherence will be more heavily targeted in CBT. If, however, they are using tobacco in the context of adherent use, the algorithm will suggest an alternative medication regimen if possible (e.g., switching from single-formulation NRT to dual-NRT).

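### Aim 3 verifies abstinence by salivary cotinine at 10 ng/ml or below with no exception for nicotine medication, so a tobacco-abstinent participant on NRT when sampled can fail verification

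*Combined protocol and SAP*

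**What the plan says.** The rule is in Aim 3 Methods, Procedures. The outcomes are set first: "Secondary smoking outcomes will include 7- and 30-day point prevalence abstinence at each assessment". The next sentence gives the test: "Abstinence will be verified by salivary cotinine assay (≤ 10 ng/ml), which improves self-report validity". CO is then added conditionally: "When in-person visits are allowed post-COVID-19 pandemic, participants will also be asked to provide expired carbon monoxide (CO) breath readings". It has no cut-off, and nothing says how it combines with cotinine. Table 1 (29 rows) has no row for either biomarker, so it supplies no exception.

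NRT belongs to the treatment under study. Table 2 has algorithm rows that begin "Quit Week Algorithm for Revising Pharmacotherapy Regimen (Initially Prescribed Dual-NRT" and "Quit Week Algorithm for Revising Pharmacotherapy Regimen (Initially Prescribed Single-Formulation NRT", alongside rows for varenicline and bupropion. The section on personalized pharmacotherapy gives, as its example of a regimen change, "switching from single-formulation NRT to dual-NRT". The algorithm only recommends; the participant's VA providers decide what to prescribe.

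Table 1, row 19, schedules medication adherence ("Visual Analog Scale (personalized to pharmacotherapy use") at the quit date and at months 3 and 6. Row 21 schedules 7- and 30-day abstinence at the same two follow-ups.

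**The concern.** Cotinine is formed from nicotine whether it comes from tobacco or from a patch, gum, lozenge or inhaler. The assay therefore cannot tell continued tobacco use from NRT. Read literally, the rule can fail a participant who has stopped tobacco and is using a medication that the intervention itself may have suggested. Participants on varenicline or bupropion alone do not face this error, so verified rates could differ by regimen for reasons unrelated to tobacco use.

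At stake is the Aim 3 verified quit rate. The error acts in one direction: it understates abstinence. A low verified rate in a 15-person development cohort could be read as weak early promise when part of it came from the verification rule.

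**Working it through.** The plan states no quit rate, error rate or power figure for this outcome, so there is no figure to reproduce. The check is a reading of the rule followed by a sizing.

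**Reading**

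1. Rule: cotinine of 10 ng/ml or below verifies abstinence (Aim 3 Procedures). No sentence or table exempts nicotine-medication users.
2. Exposure: single and dual NRT are possible regimens (Table 2 and the pharmacotherapy section). Whether anyone is on NRT at a given sample is not stated, and no duration of NRT is given.
3. Alternative test: CO is taken only when in-person visits are allowed, and has no cut-off or deciding role.
4. It follows that a participant who is tobacco-abstinent, on NRT at sampling and above 10 ng/ml is not verified, and nothing in the text corrects this.

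**Size per affected participant**

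Aim 3 plans 3 cohorts of 5, so N = 15. One participant is 1/15 = 6.7 percentage points. The plan does not state the denominator of the quit rate; 15 is an assumption.

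**Illustration with assumed counts**

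Let A be the number truly abstinent and k the number of those affected. The verified rate is (A − k)/15.

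| A | k = 0 | k = 1 | k = 2 | k = 3 | Exact 95% CI at k = 0 |
|---|---|---|---|---|---|
| 5 | 33.3% | 26.7% | 20.0% | 13.3% | 11.8% to 61.6% |
| 3 | 20.0% | 13.3% | 6.7% | 0.0% | 4.3% to 48.1% |

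All but one of the shifted rates stay inside the sampling interval of the unshifted rate. The exception is A = 3 with k = 3, where 0% lies below the lower limit of 4.3%.

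**The same question with assumed rates**

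Let q be the true quit rate, f the share of quitters on NRT at sampling, and s the chance that cotinine exceeds 10 ng/ml on NRT. The documents give none of these.

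- Expected verified rate = q × (1 − f × s). With q = 20%:
  - f = 10%, s = 0.5 gives 0.20 × 0.95 = 19%.
  - f = 50%, s = 1 gives 0.20 × 0.50 = 10%.
- Chance of losing at least one true quitter among 15 = 1 − (1 − q × f × s)^15:
  - q = 10%, f = 10%, s = 0.5 gives 1 − 0.995^15 = 7%.
  - q = 30%, f = 50%, s = 1 gives 1 − 0.85^15 = 91%.

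The range is this wide because the inputs are unknown. It shows that the effect could be negligible or material, not which is more likely.

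**Aim 4**

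Table 3 bases the abstinence outcomes on the timeline follow-back. The Aim 4 analysis describes the proportion who quit in each arm, without a test and without mentioning either biomarker. The bias as written is 0 points.

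**The case against.** The strongest reply is that little hangs on the verified rate. The Aim 3 analysis section covers qualitative feedback and usability problems, and revision between cohorts rests on qualitative data. No stated step uses a quit rate. That stands, and it is why the point is minor. It does not remove the point, because the plan names abstinence as an outcome and gives a rule that can misclassify it.

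A second reply is that NRT use at sampling is not shown. That also stands in part. Row 19 shows that medication is asked about at months 3 and 6, not that NRT is expected then; it could equally concern varenicline or bupropion. The number affected may be zero.

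A third reply is that the planned CO readings deal with the problem. They could, but no text gives them that role, and they depend on in-person visits.

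A reader might also infer that the Aim 4 comparison is biased, since Table 3 collects cotinine and CO. The documents do not support this: abstinence there rests on the timeline follow-back, and nothing carries the Aim 3 cut-off across. Nor should the biomarkers be called purposeless. The Background criticises an earlier trial for lacking biochemical verification, so the intention can be inferred; only the rule for using them is unstated.

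**Conclusion.** The point holds for Aim 3 and is minor. As written, the cotinine rule can class a tobacco-abstinent NRT user as not abstinent, and so bias the verified 7- and 30-day rates downward. The size is about 6.7 points per affected participant if the denominator is 15. The number affected is unknown and may be zero, and every quit rate tabulated here is an illustration.

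The conclusion rests on one fact outside the documents, that cotinine does not distinguish sources of nicotine. This is general pharmacology and not a cited figure.

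It would be too strong to say that the Aim 3 quit rate will be wrong, or that any test, power statement or feasibility conclusion is affected. The outcome is secondary and descriptive, and Aim 4 rules out efficacy analyses.

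**What to change.** Add a short verification rule to Aim 3 Procedures:

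- For a participant who reports abstinence and current nicotine medication at the sample, cotinine above 10 ng/ml alone does not count as failed verification.
- Where exhaled CO is taken in person, it decides, at a cut-off fixed in advance.
- Where there is no CO reading, the participant is classed as *self-reported abstinent, not verifiable*.
- Report self-reported abstinence, verified abstinence and the number not verifiable.

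Do not use Table 1, row 15 ("Non-Cigarette Smoking Behavior"), to excuse a raised CO. As named, it may include cigars or other tobacco.

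For Aim 4, one conditional sentence is enough: if cotinine results are used to verify abstinence, the same exception for nicotine medication applies.

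The cost is a few sentences, a CO cut-off and extra table columns, with no new assay or visit. One short item on current nicotine medication may be needed with the saliva sample, because row 19 measures adherence and may not establish what is being used that day. The downside is that some abstinence claims will be labelled not verifiable. Treatment and prescribing are unchanged.

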Personalized Annie Messaging Support. If the participant has a working cell phone and is willing to receive SMS text messages, supportive SMS text messages will be sent to the participant starting after Session 1 and extending through 6 months post-quit. Individual tailoring of follow-up messages will be based upon the post-quit patient mHealth survey, which will measure the following: desired frequency of messages (1-3 per day); specific abstinence-related concerns (i.e., weight gain, difficulty coping with stress); preferred types of messages (skills-focused, health informational, encouragement); and personalized reasons for staying quit. Participants can opt out of follow-up messaging at any point. All messages will be sent via the VA Annie texting capability. As stated above, Annie is a standard VA SMS text message capability designed to promote Veteran self-care.

AIM 4 – PILOT FEASIBILITY RANDOMIZED CONTROL TRIAL (RCT)

The proposed RCT is a two-arm experimental design to demonstrate the feasibility of a larger trial and the acceptability of the intervention design. Participants ($N = 30$) will be stratified by clinic and randomized to either the active treatment or to standard of care VA Quitline (telehealth intervention including 5 sessions of CBT) plus SmokefreeVET (text-messaging intervention). The comparison group was selected in order to assess the feasibility of recruitment, retention, and randomization procedures. We will assess acceptability of the active treatment among patients, providers, and key VA stakeholders.

SAMPLE RECRUITMENT

A total of $N = 30$ will be enrolled in the study. Participants will be recruited from the Durham VAHCS. Inclusion criteria are: Durham VA patient, willing to complete study procedures, appointment in Durham

Tobacco Cessation Treatment Preferences among Veteran Smokers

VA Infectious Disease (ID) Clinic or Durham VA Cardiology Section within the past 12 months, and currently smoking ≥ 7 times per week (cigarettes, cigars, cigarillos, hookah, etc.) and/or using ≥ 1 can of smokeless tobacco per week. Exclusion criteria are: participation in Aim 3 (already received the intervention), current hospitalization (recent hospitalization is acceptable), currently not using combustible or smokeless tobacco (vaping only), acute risk for suicide documented in the medical record, or inability to complete study procedures.

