We will recruit in several different ways. First, clinicians in the ID Clinic and Cardiology Section can provide a direct study referral by adding the PI and/or Project Coordinator as a co-signer to a CPRS notes. Second, study information sheets will be made available in ID Clinic and Cardiology Service clinical spaces for potential participants to peruse and self-refer to the study. Third, potential participants with documented tobacco use within the past 2 years who have been seen within the past 2 years in the ID Clinic or Cardiology Service will be sent an introductory letter signed by the PI that describes the study and invites participation. Veterans who do not decline will be called to determine interest in the study and basic study eligibility.

PROCEDURES

Screening

Veterans who are interested in study participation will be screened via telephone or in clinic for study inclusion criteria. Potential participants will be asked questions regarding current weekly tobacco use and current hospitalization at any location, and CPRS documentation will be screened to ensure the Veteran is a patient in one or both of the identified clinics, is not currently hospitalized at Durham VA, and does not have a high-risk suicide flag in their chart. Potential participants will then complete informed consent with a trained study staff member. Where possible, we will utilize DocuSign to obtain informed consent and HIPAA authorization. Immediately following screening and informed consent (Session 0), patients will complete baseline measures and randomization.

Communication with Enrolled Participants

Communication with enrolled participants will take place via mail, telephone, VA Video Connect, another approved telehealth platform (<http://vaww.telehealth.va.gov/technology/covid19-tech.asp>), or Azure RMS (in accordance with guidance issued in VA document “Use of Protected Health Information in Microsoft Office Applications”).

Measures

Table 3 describes the measures that will be used in Aim 4 as well as their administration schedule. Whenever possible, we have selected Common Data Elements from the PhenX Toolkit (Hamilton et al., 2011; Version 13.3) in order to maximize the impact of the proposed study.

Table 3. Aim 4 RCT Measures

Measure	Completed by	Time Point		
		Baseline	3-Month Follow Up	6-Month Follow Up
BACKGROUND AND PROCESS VARIABLES				
1. Demographics	Self-report	X	-	-
2. Tobacco use history/current tobacco use	Self-report	X	-	-

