Immediately following completion of baseline measures, participants will be randomized 1:1 to either the active treatment (Mesh) or to a best practice comparison condition (described below). Randomization will be concealed, stratified, and blocked. Given the two separate recruitment settings, randomization will be stratified by clinical setting (ID clinic and cardiology). For participants who are involved in both clinical settings, stratification arm will be decided by a virtual coin toss (<https://cgi.cs.duke.edu/~des/vct/vct.cgi>). In order to ensure consistent referrals for sessions with intervention facilitators, randomization will be blocked for every five participants recruited. Allocation to study condition will be computer-generated in random blocks of four and six, with the allocation block sizes and sequence only accessible by a non-investigator study staff member who is not involved in study recruitment or treatment delivery.

Intervention Arms

Participants randomized to the Mesh treatment arm will be scheduled for a first session with a quit facilitator within 10 business days of randomization. See section above “Mesh Treatment Components” for a description of the intervention arm, which includes personalized recommendations for tobacco cessation pharmacotherapy, 5 to 7 sessions, and Annie messaging. Participants will be asked to select their preferred frequency of Annie messaging: standard (about 3 times per day) or low (about 1 time per day). Study therapists will be asked to audio record a selection of sessions. A random sample of sessions will be selected for fidelity rating by a PhD-level study staff member.

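### Do the 12-month, 2-year and undated descriptions of clinic contact in Aim 4 leave eligibility or the randomization strata in doubt?

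*Combined protocol and SAP*

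**What the plan says.** The combined protocol and SAP mentions contact with the two clinics at four points in Aim 4.

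- **Inclusion criteria (Sample Recruitment).** An appointment is required in the Durham "VA Infectious Disease (ID) Clinic or Durham VA Cardiology Section within the past 12 months".
- **Letter route (Sample Recruitment).** This is the third of three recruitment routes. Documented tobacco users "who have been seen within the past 2 years in the ID Clinic or Cardiology Service will be sent an introductory letter". The next step is: "Veterans who do not decline will be called to determine interest in the study and basic study eligibility".
- **Screening.** Interested Veterans are "screened via telephone or in clinic for study inclusion criteria". Among the listed items, "CPRS documentation will be screened to ensure the Veteran is a patient in one or both of the identified clinics". That item carries no time window.
- **Randomization.** Clinic is the stratification factor, and "For participants who are involved in both clinical settings, stratification arm will be decided by a virtual coin toss". No window is given here either. Within this scheme "participants will be randomized 1:1 to either the active treatment (Mesh) or to a best practice comparison condition".

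The Aim 4 paragraph under Data Analyses limits the work to describing feasibility and acceptability. It rules out efficacy analyses, including any test of abstinence between arms.

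**The concern.** A reader who sets these sentences together finds one concept, being a patient of a clinic, with a 12-month window, a two-year window and no window. Two things could go wrong.

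First, eligibility. If staff worked from the mailing list or the undated chart item, someone last seen between 12 and 24 months ago might be enrolled against the inclusion criterion.

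Second, stratification. Take a participant with a Cardiology appointment 6 months ago and an ID visit 18 months ago. With a 12-month window this person belongs only to Cardiology. With a longer window, or none, the person counts as dual-clinic and a coin toss decides. Two staff members could handle the same case differently, so the clinic strata would lack one fixed meaning in a trial of 30.

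**Working it through.** The protocol gives no figure to reproduce on this point, so the check is mainly a comparison of what each sentence does.

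| Place in Aim 4 | Window | Function |
|---|---|---|
| Inclusion criteria | 12 months | Decides who may enrol |
| Letter route | 2 years | Decides who is contacted, on one of three routes |
| Chart check | none stated | One item in a screen against the inclusion criteria |
| Stratum rule | none stated | Decides when a coin toss sets the stratum |

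**Eligibility.** Someone seen only 18 months ago may receive a letter. The call then checks basic eligibility, and screening applies the inclusion criteria, which this person fails. A mailing list wider than the eligible population contradicts nothing when a check follows. The undated chart item sits in a paragraph whose opening sentence brings in all the inclusion criteria. Its list is also plainly abbreviated, since it does not mention the exclusion for taking part in Aim 3. The missing window reads as shorthand, not as a second rule.

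**Stratum.** The inclusion criterion is met by an appointment in either clinic, so it does not settle what counts as contact with the second. Here the text is open. Let k be the number of participants with a qualifying appointment in one clinic and only older contact in the other. The documents give no value for k, so 0 to 6 is an assumption used only to show scale. With a fair coin, the expected number placed in the other clinic's stratum is k/2, and the chance of at least one is 1 − 0.5^k.

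| k | Expected number, k/2 | Share of 30 | Chance of at least one |
|---|---|---|---|
| 0 | 0 | 0% | 0% |
| 1 | 0.5 | 0.5/30 = 1.7% | 1 − 0.5 = 50% |
| 2 | 1.0 | 1/30 = 3.3% | 1 − 0.25 = 75% |
| 4 | 2.0 | 2/30 = 6.7% | 1 − 0.0625 = 94% |
| 6 | 3.0 | 3/30 = 10% | 1 − 0.0156 = 98% |

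Under the 12-month reading every entry is zero.

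**What follows from a different stratum label.** The chance of Mesh is one half in either stratum, so the label does not change a participant's chance of either arm. Only a staff member outside recruitment and treatment delivery can see the sequence, so choosing a stratum gives no means of steering the arm. What can loosen is balance by clinic. With the stated allocation blocks of four and six, the arms within one stratum's list can differ by at most 6/2 = 3. If m participants sit in the other clinic's list, the difference counted by the recently attended clinic can reach at most 3 + m. The coin toss already accepts the same loosening for every undisputed dual-clinic participant.

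**What uses the strata afterwards.** The Aim 4 analysis paragraph lists recruitment, retention, withdrawals, satisfaction, app use and the proportion quitting in each arm. None is planned by clinic, and none is tested.

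**The case for a change.** The best case for a change starts from the purpose of the pilot. Aim 4 says it will assess whether the randomization procedures are workable, so a stratum rule that two people could apply differently touches something the pilot is meant to examine. The phrase triggers an action and is nowhere defined, and patients with second-clinic contact 12 to 24 months old can plausibly occur. The remedy would be a few words.

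It can be added that recruitment is a described outcome, and that letters to people outside the 12-month criterion would inflate a count of those invited.

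The first argument stands as far as it goes: the phrase is undefined, and staff should settle one reading before they meet such a case. The natural reading is the 12-month window, the only definition of clinic contact that applies to every enrolled participant. The two-year window has little claim to govern the stratum rule, because the Randomization section does not refer to the mailing list and referred or self-referred participants never pass through it. A looser, undated reading remains possible, but it alters only a label.

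The recruitment argument does not carry. The protocol defines no recruitment rate per letter, so no stated quantity is distorted. Reporting recruitment by route and stage would be informative, but it is a reporting preference unrelated to the stratum wording. Narrowing the mailing window would shrink the list without improving eligibility, which screening already protects.

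**Conclusion.** The concern does not call for a change. On eligibility there is no conflict: one criterion, a wider contact list, and a screen between them. On stratification there is a small gap in detail that study staff can fill sensibly with the 12-month appointment, recorded in their working instructions.

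The gap affects an unknown and possibly zero number of the 30 participants. For each of them it means a 50% instead of a 0% chance of carrying the other clinic's stratum label. It leaves the allocation ratio, the concealment and every planned summary as they are.

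This rests on three things in the protocol: screening is done against the full inclusion criteria, the allocation sequence stays hidden from recruiting and treating staff, and Aim 4 stays descriptive with no analysis by clinic. If a by-clinic comparison were added later, the definition of the strata would need to be explicit.
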